15.2.3. Severity of Events

The severity of AEs and SAEs will be graded using the National Cancer Institute CTCAE (version 4). Any AE not listed in the CTCAE will be graded as follows:

CONFIDENTIAL

The information contained herein may not be used, disclosed, or published without the written consent of Biogen MA Inc.

Severity of Event	
Grade	Definition
1	Mild AE
2	Moderate AE
3	Severe or medically significant AE
4	Life-threatening AE
5	Death related to AE

15.2.4. Expectedness of Events

Expectedness of all AEs will be determined by the Sponsor according to the Investigator's Brochure.

15.3. Monitoring and Recording Events

15.3.1. Adverse Events

Any AE experienced by the participant between the time of first dose of study treatment and the last study visit is to be recorded on the CRF, regardless of the severity of the event or its relationship to study treatment. At each study visit, post-LP telephone contact, and the Final or Early Termination Visit, the Investigator will assess the participant for AEs and will record any new AEs or updates to previously reported AEs on the CRF.

AEs that are ongoing when the participant completes or discontinues the study will be followed by the Investigator until the event has resolved, stabilized, or returned to baseline status. AE outcome will not be recorded on the CRF.

15.3.2. Serious Adverse Events

Any SAE experienced by the participant between the time of the signing of the ICF and the final study visit is to be recorded on an SAE form, regardless of the severity of the event or its relationship to study treatment. SAEs must be reported to the Sponsor within 24 hours or according to national law as described in Section 15.3.3. Follow-up information regarding an SAE also must be reported with 24 hours.

Participants will be followed for all SAEs until the final study visit. Thereafter, the event should be reported to the Sponsor only if the Investigator considers the SAE to be related to study treatment.

Any SAE that is ongoing when the participant completes or discontinues the study will be followed by the Investigator until the event has resolved, stabilized, or returned to baseline status.

CONFIDENTIAL

The information contained herein may not be used, disclosed, or published without the written consent of
Biogen MA Inc.

15.3.3. Immediate Reporting of Serious Adverse Events

In order to adhere to all applicable laws and regulations for reporting an SAE, the study site must formally notify the Sponsor within 24 hours of the study site staff becoming aware of the SAE or according to national law. It is the Investigator's responsibility to ensure that the SAE reporting information and procedures are used and followed appropriately.

Reporting Information for SAEs

A report **must be submitted** to the Sponsor regardless of the following:

- Whether or not the participant has undergone study-related procedures
- Whether or not the participant has received study treatment
- The severity of the event
- The relationship of the event to study treatment

To report initial or follow-up information on an SAE, fax a completed SAE form; refer to the Study Reference Guide for complete contact information.

15.3.3.1. Deaths

Death is an outcome of an event. The event that resulted in death should be recorded on the appropriate CRF. All causes of death must be reported as SAEs within 24 hours of the site becoming aware of the event or according to national law. The Investigator should make every effort to obtain and send death certificates and autopsy reports to the Sponsor. The term death should be reported as an SAE only if the cause of death is not known and cannot be determined.

15.3.4. Suspected Unexpected Serious Adverse Reactions

SUSARs are SAEs that are unexpected and judged by the Investigator or the Sponsor to be related to the study treatment administered.

Appropriate personnel at the Sponsor will unblind SUSARs for the purpose of regulatory reporting. The Sponsor will submit SUSARs (in blinded or unblinded fashion) to regulatory agencies according to local law. The Sponsor will submit SUSARs to Investigators in a blinded fashion.

The Sponsor will report SUSARs to the appropriate regulatory authorities and Investigators as required, according to local law.

CONFIDENTIAL

The information contained herein may not be used, disclosed, or published without the written consent of
Biogen MA Inc.

15.4. Procedures for Handling Special Situations

15.4.1. Pregnancy

Participants should not become pregnant during the study and for 5 months after their last dose of study treatment. If a female participant becomes pregnant, study treatment must be discontinued *immediately*.

The Investigator must report a pregnancy occurring in a female participant by faxing or emailing the appropriate form to the Sponsor within 24 hours of the study site staff becoming aware of the pregnancy; refer to the Study Reference Guide for complete contact information. The Investigator or study site staff must report the outcome of the pregnancy to the Sponsor. A pregnancy is not considered an AE and should not be recorded on the AE CRF.

Congenital abnormalities and birth defects in the offspring of male or female participants should be reported as an SAE if conception occurred during the study treatment period.

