7.2. Overall Study Duration and Follow-Up

The overall duration of study participation for a single participant will be up to 368 weeks, which includes an approximately 4-week screening period, up to a 360-week treatment period, and a 4-week follow-up period.

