7.2.3. Follow-Up

Participants will return for their final visit, which will be 4 weeks after their last dose. Participants who withdraw from the study early will return for an Early Termination Visit, which will be 4 weeks after their last dose.

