8. SELECTION OF PARTICIPANTS

8.1. Inclusion Criteria

To be eligible to participate in this study, candidates must meet the following eligibility criteria at Screening, or at the time point specified in the individual eligibility criterion listed:

1. Ability of the participant to understand the purpose and risks of the study and indicate consent, and ability of the participant or his/her legally authorized representative to provide signed and dated informed consent and authorization to use PHI in accordance with national and local participant privacy regulations.
2. Must have diagnosis of SOD1-ALS and must have completed the End of Study Visit for either Parts A, B, or C of Study 233AS101 (i.e., were not withdrawn).
3. If taking riluzole, participant must be receiving a stable dose for ≥ 30 days prior to Day 1.
4. If taking edaravone, participant must have initiated edaravone ≥ 60 days (2 treatment cycles) prior to Day 1. Edaravone may not be administered on dosing days during this study.
5. Medically able to undergo the study procedures, and to adhere to the visit schedule at the time of study entry, as determined by the Investigator.
6. Must have screening values of coagulation parameters including platelet count, INR, PT, and aPTT within normal ranges. Coagulation tests may be repeated at the local laboratory once if, in the opinion of the Investigator, values of the initial tests are out of range but deemed not clinically significant. Participants with nonclinically significant and stable out-of-range values may be eligible to enroll in the study at the discretion of the Investigator. (For normal ranges, please refer to the Study Reference Guide).
7. Female participants of childbearing potential must agree to practice effective contraception during the study and be willing and able to continue contraception for 5 months after their last dose of study treatment. For further details of contraceptive requirements for this study, please refer to (see Section 15.5).
8. Participants in Parts A and B must have a washout ≥ 16 weeks between the last dose of study treatment received in Study 233AS101 and the first dose of BIIB067 received in the current Study 233AS102. Participants in Part C do not require a washout period.

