15.5. Contraception Requirements

All women of childbearing potential must ensure that effective contraception is used during the study and for 5 months, whichever is longer, after their last dose of study treatment. In addition, female participants should not donate eggs for the duration of the study and for at least 5 months after their last dose of study treatment.

For the purposes of this study, women who do not meet one of the following criteria are considered to be physiologically capable of becoming pregnant and are, therefore, defined as women of childbearing potential:

- Postmenopausal
 - 12 continuous months of natural (spontaneous) amenorrhea without an alternative medical cause and a serum FSH level >40 mIU/mL
 - 6 weeks after surgical bilateral oophorectomy with or without hysterectomy
- Posthysterectomy
 - Female surgical sterilization (e.g., bilateral tubal ligation)

For the purposes of the study, effective contraception is defined as use of at least 1 of the following:

For females:

- Established use of oral, injected, implanted, intravaginal, or transdermal hormonal methods of contraception.
- Placement of an intrauterine device or intrauterine hormone-releasing system.
- Barrier methods of contraception with use of a spermicide: condom or occlusive cap (diaphragm or cervical/vault caps) with spermicidal foam/gel/film/cream suppository. The use of barrier contraceptives should always be supplemented with the use of a spermicide.
- Sex with a male who has undergone surgical sterilization (with the appropriate postvasectomy documentation of the absence of sperm in the ejaculate).
- True abstinence, when this is consistent with the preferred and usual lifestyle of the participant, can be considered an acceptable method of contraception based on the evaluation of the Investigator who should also take into consideration the duration of the clinical trial. Periodic abstinence (e.g., calendar, ovulation, symptothermal, postovulation methods) and withdrawal are not considered acceptable methods of contraception.

CONFIDENTIAL

The information contained herein may not be used, disclosed, or published without the written consent of
Biogen MA Inc.

Pregnancy reporting is described in Section [15.4.1](#).

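### The birth-defect SAE instruction covers conceptions during treatment only, although women must avoid pregnancy for 5 months after the last dose

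*Protocol*

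**What the plan says.** Protocol Section 15.4.1 tells participants not to become pregnant during the study or in the 5 months after the last dose. Inclusion criterion 7 (Section 8.1) requires women of childbearing potential to "be willing and able to continue contraception for 5 months after their last dose of study treatment", and Section 15.5 requires that "effective contraception is used during the study and for 5 months, whichever is longer, after their last dose of study treatment".

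The last sentence of Section 15.4.1 deals with offspring of male and female participants. It says that congenital abnormalities and birth defects "should be reported as an SAE if conception occurred during the study treatment period". That section does not define the study treatment period. Section 7.2 lists its parts separately: "up to a 360-week treatment period, and a 4-week follow-up period". Section 7.2.3 adds: "Participants will return for their final visit, which will be 4 weeks after their last dose".

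Section 15.3.2 has all SAEs recorded, whatever their cause, from consent to the final study visit. It then says: "Thereafter, the event should be reported to the Sponsor only if the Investigator considers the SAE to be related to study treatment". Where an SAE report is due, Section 15.3.3 says that "the study site must formally notify the Sponsor within 24 hours of the study site staff becoming aware of the SAE".

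For a pregnancy in a female participant, Section 15.4.1 requires a report within 24 hours of site awareness. On what follows, it says: "The Investigator or study site staff must report the outcome of the pregnancy to the Sponsor". Section 15.6.1 also makes the Investigator follow up the outcome. Neither section states a deadline for the outcome report.

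**The concern.** Two windows in the same section do not match. The protocol asks women to avoid conception for 5 months after dosing, but its only explicit instruction on offspring refers to conceptions during treatment. A site applying that sentence could reasonably decide that a birth defect from a conception in, say, the third month after the last dose needs no SAE form.

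The general SAE rule does not clearly catch the case, because by then the participant has normally had her final visit and only SAEs judged related are requested. The defect would then reach the Sponsor as a pregnancy outcome with no stated deadline, not as an SAE within 24 hours. At stake are the speed and consistency of safety reporting for a serious outcome in a period the protocol itself singles out.

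**Working it through.** No power or sample size figure is involved. The check compares reporting windows and does the date arithmetic.

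**Inputs**
- Pregnancy-avoidance window: 5 months after the last dose (Protocol 8.1 criterion 7, 15.4.1, 15.5).
- Final visit: 4 weeks = 28 days after the last dose (Protocol 7.2.3).
- Days per month: 30.4375, the conversion used in SAP Appendix A.

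**Step 1. Length of the avoidance window.** 5 × 30.4375 = 152.19, about 152 days (21.7 weeks).

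**Step 2. Post-dose days covered by the offspring instruction in 15.4.1.**

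| Reading of study treatment period | Days covered | Share | Days not covered |
|---|---|---|---|
| Ends with dosing, as Section 7.2 implies | 0 | 0/152 = 0% | 152 |
| Also includes the 4-week follow-up | 28 | 28/152 = 18% | 152 − 28 = 124 |

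**Step 3. Whether the general SAE rule fills the gap.** Take a participant whose final visit is 28 days after her last dose and who conceives on post-dose day 1 or later. At most 28 − 1 = 27 days pass between conception and that visit. A birth defect would have to be found within that time to fall under the period when all SAEs are recorded. In practice it will nearly always be found later, when the related-only rule applies. Conceptions in the last 124 days of the window (124/152 = 82%) occur after the final visit altogether.

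**Step 4. Other rules that bear on the case.**
- Section 15.1.2 makes a congenital anomaly an SAE by definition, but sets no reporting period.
- Section 15.3.3 requires SAE reports regardless of relationship, but Section 15.3.2 sets the time window and drops that breadth after the final visit.
- Sections 15.4.1 and 15.6.1 require the pregnancy and its outcome to be reported and followed in female participants, with no stated end date. The Sponsor should therefore learn of a case the site knows about.
- Section 15.3.4 lets the Sponsor judge relatedness itself, but only once it has been told.
- Section 10.1 encourages participants who stop dosing to stay in the study. For them, SAEs are recorded regardless of cause until their own final visit.

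**Step 5. Effect on the analysis.** None. AE recording ends at the last study visit (Protocol 15.3.1), and follow-up time in the incidence rates ends on the last day on study (SAP 4.9.1).

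**The case against.** The strongest reply is that this is a wording mismatch with little consequence.

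- *The sentence is not an exclusion.* It says to report if conception fell in the treatment period, not only if, and a congenital anomaly is an SAE under 15.1.2 anyway. This stands as a reading of that sentence. It does not remove the related-only limit that 15.3.2 imposes after the final visit.
- *The relatedness threshold is low.* Under 15.2.2 a reasonable possibility is enough, and temporal sequence or the lack of another explanation counts towards it. Many defects from conceptions in this window could therefore go in as SAEs within 24 hours. This narrows the gap to defects the Investigator judges unrelated, which is a real limit on its size.
- *The Sponsor is told anyway.* The pregnancy and its outcome must both be reported. This stands, and it is why the loss is one of speed and route, not of knowledge.
- *The outcome form or site instructions may set a deadline.* Those documents are not available here, so only the protocol's silence can be shown.
- *Days are not cases.* True. The documents give up to 183 participants dosed in the parent study but no number of women of childbearing potential.
- *It may be too late.* The SAP is for the closeout report and was approved in August 2024. The documents do not say whether dosing has ended. The gap lies in the months after the last dose, so a late study stage does not remove it, but an amendment may be impractical.

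**Conclusion.** The concern holds, at the lowest level of minor. The explicit offspring instruction covers 0 of about 152 post-dose days on the natural reading and at most 28 on the widest, leaving 124 to 152 days of the protocol's own avoidance window outside it. The remaining gap is narrow: a birth defect from a post-dose conception in a female participant, found after her final visit and judged unrelated. Such a case has no 24-hour SAE route and an outcome report with no stated deadline.

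This rests on reading the treatment period from Section 7.2, since 15.4.1 does not define it, and on a final visit 28 days after the last dose. No case count and no fetal risk are claimed. The primary endpoint tables do not change.

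**What to change.** - **Section 15.4.1:** split the last sentence. For offspring of female participants, require an SAE report if conception fell in the study treatment period or within 5 months after the last dose. For offspring of male participants, leave the rule as it is, because no post-dose contraception window applies to them.
- **Section 15.3.2:** after the related-only sentence, add that the limit does not apply to congenital anomalies covered by Section 15.4.1, which are reported regardless of relationship.

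Anomalies in the window then carry the 24-hour deadline of 15.3.3. Other pregnancy outcomes would still have no stated deadline.

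**Cost.** The change is to one sentence in each section, with no added visit or procedure. It does need an amendment, with ethics committee submission and regulatory submission where local law requires (Section 19.4), in about 15 countries, so it is best added to an amendment made for other reasons. Expect a few late SAE reports after the final visit, some of them unrelated.

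If no amendment is planned, a reminder to sites to report promptly the outcomes of pregnancies conceived within 5 months of the last dose would help. The wording should also be corrected in any later protocol that reuses it.

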15.4.2. Overdose

An overdose is any dose of study treatment administered to a participant or taken by a participant that exceeds the dose assigned to the participant according to the protocol. Overdoses are not considered AEs and should not be recorded as an AE on the CRF; however, all overdoses must be recorded on an Overdose form and faxed or emailed to the Sponsor within 24 hours of the site becoming aware of the overdose. An overdose must be reported to the Sponsor even if the overdose does not result in an AE. If an overdose results in an AE, the AE must be recorded. If an overdose results in an SAE, both the SAE and Overdose forms must be completed and faxed to the Sponsor; refer to the Study Reference Guide for complete contact information. All study treatment-related dosing information must be recorded on the dosing CRF.

15.4.3. Medical Emergency

In a medical emergency requiring immediate attention, study site staff will apply appropriate medical intervention, according to current standards of care. The Investigator (or designee) should contact the study's Medical Director. Refer to the Study Reference Guide's Official Study Contact List for complete contact information.

15.4.3.1. Unblinding for Medical Emergency

In a medical emergency during the Loading Dose Period, when knowledge of the participant's study treatment assignment may influence the participant's clinical care, the Investigator and, if applicable, designated site personnel at the Sponsor, may access the participant's study treatment assignment by IRT. The Investigator must document the reasons for unblinding in the participant's source documents. The Investigator is strongly advised not to divulge the participant's study treatment assignment to any individuals who are not directly involved in managing the medical emergency or to site personnel who are involved with the analysis and conduct of the study. The Investigator can contact the Sponsor or designee to discuss such situations.

CONFIDENTIAL

The information contained herein may not be used, disclosed, or published without the written consent of Biogen MA Inc.

15.5. Contraception Requirements

All women of childbearing potential must ensure that effective contraception is used during the study and for 5 months, whichever is longer, after their last dose of study treatment. In addition, female participants should not donate eggs for the duration of the study and for at least 5 months after their last dose of study treatment.

For the purposes of this study, women who do not meet one of the following criteria are considered to be physiologically capable of becoming pregnant and are, therefore, defined as women of childbearing potential:

- Postmenopausal
 - 12 continuous months of natural (spontaneous) amenorrhea without an alternative medical cause and a serum FSH level >40 mIU/mL
 - 6 weeks after surgical bilateral oophorectomy with or without hysterectomy
- Posthysterectomy
 - Female surgical sterilization (e.g., bilateral tubal ligation)

For the purposes of the study, effective contraception is defined as use of at least 1 of the following:

For females:

- Established use of oral, injected, implanted, intravaginal, or transdermal hormonal methods of contraception.
- Placement of an intrauterine device or intrauterine hormone-releasing system.
- Barrier methods of contraception with use of a spermicide: condom or occlusive cap (diaphragm or cervical/vault caps) with spermicidal foam/gel/film/cream suppository. The use of barrier contraceptives should always be supplemented with the use of a spermicide.
- Sex with a male who has undergone surgical sterilization (with the appropriate postvasectomy documentation of the absence of sperm in the ejaculate).
- True abstinence, when this is consistent with the preferred and usual lifestyle of the participant, can be considered an acceptable method of contraception based on the evaluation of the Investigator who should also take into consideration the duration of the clinical trial. Periodic abstinence (e.g., calendar, ovulation, symptothermal, postovulation methods) and withdrawal are not considered acceptable methods of contraception.

CONFIDENTIAL

The information contained herein may not be used, disclosed, or published without the written consent of
Biogen MA Inc.

Pregnancy reporting is described in Section [15.4.1](#).

15.6. Safety Responsibilities

15.6.1. The Investigator

The Investigator's responsibilities include the following:

- Monitor and record all AEs, including SAEs, regardless of the severity or relationship to study treatment.
- Determine the seriousness, relationship, and severity of each event.
- Determine the onset and resolution dates of each event.
- Monitor and record all pregnancies and follow up on the outcome of the pregnancy in female participants.
- Complete an SAE form for each SAE and fax or email it to the Sponsor within 24 hours of the study site staff becoming aware of the event or according to national law.
- Pursue SAE follow-up information actively and persistently. Follow-up information must be reported to the Sponsor within 24 hours of the study site staff becoming aware of new information or according to national law.
- Ensure all AE and SAE reports are supported by documentation in the participants' medical records.
- Pursue AE follow-up information, if possible, until the event has resolved or become stable.
- Report SAEs to local ethics committees, as required by local law.

